## **Study Identification**

**Unique Protocol ID:** HEM-3331-20-20-1

**Brief Title:** Germline Mutations Associated With Hereditary Pancreatic Cancer in Unselected Patients With Pancreatic Cancer in Mexico.

**Official Title:** Prevalence Estimation of BRCA1, BRCA2 and Other Germline Mutations Associated With Hereditary Pancreatic Cancer Using a Comprehensive Gene Panel in an Unselected Cohort of Patients With Pancreatic Adenocarcinoma in a Mexican Population.

**Document date:** Version 1.1 (20 July 2020).

prevalence of *BRCA1/2* inherited mutations in patients with pancreatic cancer in Mexican population are lacking.

Identification of *BRCA* germline mutations in patients with pancreatic cancer has implications for treatment. Recently, the POLO trial, a phase 3 trial, evaluated the efficacy of olaparib as maintenance therapy in patients who had a germline *BRCA1* or *BRCA2* mutation and metastatic pancreatic cancer without progression during first line platinum-based chemotherapy. Patients were randomized to receive maintenance olaparib or placebo. Olaparib showed longer progression-free survival than placebo (7.4 months vs. 3.8 months; hazard ratio for disease progression or death, 0.53; 95% CI, 0.35 to 0.82; P=0.004) (Golan T, et al.). On October 2018, the US Food and Drug Administration (FDA) granted orphan drug designation to olaparib for the treatment of patients with metastatic pancreatic cancer, according to the POLO trial results.

Moreover, the National Comprehensive Cancer Network (NCCN) Guidelines Version 3.2019 Pancreatic Adenocarcinoma recommends germline testing for any patient with confirmed pancreatic cancer, using comprehensive gene panels for hereditary cancer syndromes.

The identification of *BRCA* inherited mutations also allows family members to have genetic testing, counselling and possible screening in those high-risk individuals.

**Problem:**

Olaparib has recently been approved as a maintenance therapy for patients with germline *BRCA* mutation and metastatic pancreatic cancer that had not progressed during first line platinum-based chemotherapy. In the POLO trial, the reported prevalence of germline *BRCA* mutations was 7.5%. Patients from North America, Europe and the Asia-Pacific region were included. Mexico did not participate in the POLO trial. The prevalence of germline *BRCA* mutation in patients with pancreatic cancer in Mexico is unknown. Given possible therapeutic implications for patients with pancreatic cancer and opportunities for genetic counselling and screening for family members, it is mandatory to determine the prevalence of germline *BRCA* mutations in Mexican patients with pancreatic cancer.

**Justification:**

These data will highlight the importance of universal screening for germline mutations in pancreatic cancer. This will allow to identify germline mutations most frequently associated with pancreatic cancer. In addition, this knowledge will contribute to develop surveillance strategies in family members affected.

**Hypothesis:**

The prevalence of germline mutations in *BRCA1/2* genes in an unselected sample (by family history) of patients with pancreatic cancer is similar to that reported in other unselected populations.

**Objectives:**

**Primary:**

To determine the prevalence of *BRCA1* and *BRCA2* germline mutations in a cohort of patients with pancreatic adenocarcinoma.

**Secondary:**

To determine the prevalence of other germline mutations in patients with pancreatic adenocarcinoma associated with hereditary pancreatic cancer (*ATM, BRCA1, BRCA2, CDKN2A, EPCAM, MLH1, MSH2, MSH6, PALB2, PMS2, STK11*).

To describe the clinical and pathological characteristics of patients with pancreatic adenocarcinoma and *BRCA1, BRCA2* and other germline mutations.

To provide oncologic and genetic counselling for patients with pancreatic adenocarcinoma and germline mutations.

To establish a registry of family members of mutated patients eligible for genetic testing and provide appropriate cancer screening strategies for previvors or asymptomatic carriers.

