**Study design:**

This is an observational, cross-sectional study. Prevalence will be determined by testing all consecutive patients with histologic diagnosis of pancreatic adenocarcinoma (PAC) regardless of family history, clinical stage and treatment. In other words, the prevalence will be determined in an unselected patient population. To decrease potential survivorship bias, we will include only patients with PAC within 6 months of diagnosis. Participants will provide informed consent and they will allow access to medical records. Patients' demographics and cancer treatment information will be obtained from questionnaires completed by the participants and/or abstracted from medical records. A clinical geneticist will evaluate all patients, with emphasis on the cancer family history. They will provide a blood sample from peripheral access for DNA analysis; 10 mL of whole blood mixed with EDTA will be collected from each patient. We will use a commercial panel (Invitae Multi-Cancer Panel®) for DNA analyses.

Invitae Multi-Cancer Panel® analyzes 84 genes associated with hereditary cancers, including all genes specifically associated with hereditary pancreatic cancer. Invitae is a College of American Pathologist (CAP)-accredited and Clinical Laboratory Improvement Amendments (CLIA)-certified clinical diagnostic laboratory performing full-gene sequencing and deletion/duplication analysis using next-generation sequencing technology (NGS). The Invitae Multi-Cancer Panel includes 84 genes: *AIP, ALK, APC, ATM, AXIN2, BAP1, BARD1, BLM, BMPR1A, BRCA1, BRCA2, BRIP1, CASR, CDC73, CDH1, CDK4, CDKN1B, CDKN1C, CDKN2A, CEBPA, CHEK2, CTNNA1, DICER1, DIS3L2, EGFR, EPCAM, FH, FLCN, GATA2, GPC3, GREM1, HOXB13, HRAS, KIT, MAX, MEN1, MET, MITF, MLH1, MSH2, MSH3, MSH6, MUTYH, NBN, NF1, NF2, NTHL1, PALB2, PDGFRA, PHOX2B, PMS2, POLD1, POLE, POT1, PRKAR1A, PTCH1, PTEN, RAD50, RAD51C, RAD51D, RB1, RECQL4, RET, RUNX1, SDHA, SDHAF2, SDHB, SDHC, SDHD, SMAD4, SMARCA4, SMARCB1, SMARCE1, STK11, SUFU, TERC, TERT, TMEM127, TP53, TSC1, TSC2, VHL, WRN, WT1*. Genes are tested for punctual variations in the sequence and for deletion/duplication using Next Generation Sequencing, and Multiplex Ligation Probe Amplification, respectively.

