**Statistical methods:**

This is an observational, cross-sectional study. To estimate the prevalence of *BRCA1* and *BRCA2* germline mutations in unselected pancreatic cancer patients, a sample size of 107 patients is required assuming a prevalence of 7.5%, precision of 5% and 95% Confidence Interval. We use a formula for a prevalence survey, with finite population correction.

*BRCA1* and *BRCA2* prevalence will be defined as the proportion of patients with pathogenic germline mutations in *BRCA1/BRCA2*. Prevalence will be presented as percentage.

Prevalence of other germline mutations will be defined as the proportion of patients with pathogenic germline mutations in genes previously identified as increasing pancreatic cancer susceptibility. Prevalence will be presented as percentage.

Clinical and family history descriptive statistics will be calculated for study variables stratified by BRCA mutation status (positive or negative). The Fisher's exact test will be used to compare the distribution of selected categorical variables between BRCA- positive or negative patients. All statistical tests are two-sided with a statistical significance level of  $P \leq 0.05$ . All statistical analyses will be performed using IBM SPSS Statistics Version 21.

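### Does the outcome on other germline mutations need a new definition because its gene list includes BRCA1 and BRCA2?

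*Combined protocol and SAP*

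**What the plan says.** Four places in the combined protocol and SAP bear on the point.

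- **Objectives, Primary.** The target is BRCA1 and BRCA2 "germline mutations in a cohort of patients with pancreatic adenocarcinoma".
- **Objectives, Secondary, first item.** The target is the "prevalence of other germline mutations in patients with pancreatic adenocarcinoma associated with hereditary pancreatic cancer (*ATM, BRCA1, BRCA2, CDKN2A" and onwards. The full parenthesis reads "ATM, BRCA1, BRCA2, CDKN2A, EPCAM, MLH1, MSH2, MSH6, PALB2, PMS2, STK11": 11 genes, of which BRCA1 and BRCA2 are two.
- **Statistical methods.** BRCA prevalence has its own paragraph. The next paragraph covers the secondary outcome in these words: "other germline mutations will be defined as the proportion of patients with pathogenic germline mutations in genes previously identified as increasing pancreatic cancer", where the sentence goes on to refer to susceptibility. It names no genes, does not refer back to the objective, and does not say whether the proportion is pooled or given gene by gene.
- **Study design.** The commercial panel "analyzes 84 genes associated with hereditary cancers, including all genes specifically associated with hereditary pancreatic cancer". All 84 are named, but the pancreatic subset is not marked.

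Two further places show how the document uses the word *other*. The official title under Study Identification begins "Prevalence Estimation of BRCA1, BRCA2 and Other Germline Mutations Associated With Hereditary Pancreatic Cancer". The second secondary objective concerns "patients with pancreatic adenocarcinoma and *BRCA1, BRCA2* and other germline mutations".

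**The concern.** In a prevalence study the definition of the numerator largely determines the result. Here the numerator of a named secondary outcome appears to be defined twice. The objective gives a closed list that contains the primary-outcome genes, so BRCA carriers could be counted again under the heading of other mutations. The analysis section gives a verbal description that could admit panel genes outside the list, and the text does not fix which ones before results arrive. Two analysts, each following one section to the letter, might report different percentages from the same 107 patients.

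**Working it through.** **Inputs.** From Statistical methods: n = 107, assumed BRCA1/2 prevalence 7.5%, precision 5 percentage points, 95% confidence. From Objectives, Secondary: the 11-gene list. From Study design: the 84-gene panel. The documents give no expected prevalence for non-BRCA mutations, so 3%, 5% and 10% are used below as assumptions.

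**1. The plan's own figure.** The plan states "a sample size of 107 patients is required assuming a prevalence of 7.5" per cent. The single-proportion precision formula gives

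n = 1.96² × 0.075 × 0.925 / 0.05² = 106.6, rounded up to 107.

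This matches the stated size before any finite population correction. It depends only on the primary outcome, so the wording of the secondary outcome cannot alter it.

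**2. Gene counts.** The panel has 84 distinct genes and all 11 listed genes are on it. Removing BRCA1 and BRCA2 leaves 11 − 2 = 9: ATM, CDKN2A, EPCAM, MLH1, MSH2, MSH6, PALB2, PMS2 and STK11. Panel genes outside the list number 84 − 11 = 73.

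**3. Size of the BRCA overlap if the list is taken literally and pooled.** Expected BRCA carriers: 107 × 0.075 = 8.0, with a central 95% binomial range of 3 to 14. If no patient carries both kinds of variant, they add 7.5 points. If the two kinds are independent and non-BRCA prevalence is x, they add 7.5 × (1 − x) points:

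| Assumed non-BRCA prevalence | Points added | Pooled figure |
|---|---|---|
| 3% | 7.275 | 10.3% |
| 5% | 7.125 | 12.1% |
| 10% | 6.75 | 16.75% |

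If prevalence is reported gene by gene, nothing is added.

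**4. Size of the open-list question.** Each patient whose only pathogenic variant lies outside the list moves the figure by 1/107 = 0.93 points. The documents do not say how many such patients to expect, so a total cannot be given.

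**5. Which reading the text supports.**

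- In the objective, the parenthesis directly follows the reference to hereditary pancreatic cancer. It reads naturally as a list of the genes linked to that condition, where BRCA1 and BRCA2 belong. The word *other* then removes the two already covered by the primary objective.
- The title and the second secondary objective both set BRCA1 and BRCA2 beside *other* mutations, as separate groups.
- Statistical methods gives the two prevalences separate paragraphs, and it stratifies the descriptive tables and the Fisher tests by BRCA status.
- The verbal definition in Statistical methods contains no genes, so there is no second gene set to conflict with the first. The only pancreatic gene list in the available text is the one in the objective, and that is where the description most naturally points.

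Taken together, these lead to the nine non-BRCA genes.

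**The case for a change.** The best argument for a change is that the text does not state this reading outright. With a 5% non-BRCA prevalence, the two readings give about 5% or about 12%, and that gap exceeds the 5-point precision used to size the primary estimate. If the analysis section is shorthand for the objective's list, the BRCA overlap passes into the analysis definition; if it is not, the gene set stays open across 73 further panel genes. The repair would be a few words and would need no new data.

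The factual part of this stands: BRCA1 and BRCA2 are in the parenthesis, and the cross-reference is absent. The dilemma is weaker than it looks, because *other* qualifies the outcome in both sections; shorthand for the list therefore still means the list without the two primary genes. The 7-point gap needs the least plausible reading of the objective and also a pooled proportion that the plan does not specify. Even then a reader could see the cause, because BRCA prevalence is the primary result and is reported anyway. On the open list, part of the background is missing from the available text, so a gene list there cannot be ruled out. A low cost does not by itself justify a change that would only write down what an analyst would do.

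**Conclusion.** No change is needed. The inclusion of BRCA1 and BRCA2 in the list is a drafting slip, and the missing cross-reference is a detail that analysts can fill sensibly from the rest of the document. The largest effect that can be calculated, about 7 points (6.75 to 7.5 over the assumptions shown), arises only if the list is read literally and its genes are pooled; it is zero if results are given gene by gene. The effect of genes outside the list is 0.93 points per patient, with no basis in the documents for a total.

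The outcome concerned is descriptive. The study hypothesis is about BRCA1/2 alone, no test rests on the non-BRCA figure, and no sum of the two prevalences is planned. The primary prevalence, the sample size of 107 and the Fisher comparisons by BRCA status do not change. This conclusion rests on reading *other* as the title and the second secondary objective use it, and on the gene list in the objective being the one that the analysis section has in mind.

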**Study design:**

This is an observational, cross-sectional study. Prevalence will be determined by testing all consecutive patients with histologic diagnosis of pancreatic adenocarcinoma (PAC) regardless of family history, clinical stage and treatment. In other words, the prevalence will be determined in an unselected patient population. To decrease potential survivorship bias, we will include only patients with PAC within 6 months of diagnosis. Participants will provide informed consent and they will allow access to medical records. Patients' demographics and cancer treatment information will be obtained from questionnaires completed by the participants and/or abstracted from medical records. A clinical geneticist will evaluate all patients, with emphasis on the cancer family history. They will provide a blood sample from peripheral access for DNA analysis; 10 mL of whole blood mixed with EDTA will be collected from each patient. We will use a commercial panel (Invitae Multi-Cancer Panel®) for DNA analyses.

Invitae Multi-Cancer Panel® analyzes 84 genes associated with hereditary cancers, including all genes specifically associated with hereditary pancreatic cancer. Invitae is a College of American Pathologist (CAP)-accredited and Clinical Laboratory Improvement Amendments (CLIA)-certified clinical diagnostic laboratory performing full-gene sequencing and deletion/duplication analysis using next-generation sequencing technology (NGS). The Invitae Multi-Cancer Panel includes 84 genes: *AIP, ALK, APC, ATM, AXIN2, BAP1, BARD1, BLM, BMPR1A, BRCA1, BRCA2, BRIP1, CASR, CDC73, CDH1, CDK4, CDKN1B, CDKN1C, CDKN2A, CEBPA, CHEK2, CTNNA1, DICER1, DIS3L2, EGFR, EPCAM, FH, FLCN, GATA2, GPC3, GREM1, HOXB13, HRAS, KIT, MAX, MEN1, MET, MITF, MLH1, MSH2, MSH3, MSH6, MUTYH, NBN, NF1, NF2, NTHL1, PALB2, PDGFRA, PHOX2B, PMS2, POLD1, POLE, POT1, PRKAR1A, PTCH1, PTEN, RAD50, RAD51C, RAD51D, RB1, RECQL4, RET, RUNX1, SDHA, SDHAF2, SDHB, SDHC, SDHD, SMAD4, SMARCA4, SMARCB1, SMARCE1, STK11, SUFU, TERC, TERT, TMEM127, TP53, TSC1, TSC2, VHL, WRN, WT1*. Genes are tested for punctual variations in the sequence and for deletion/duplication using Next Generation Sequencing, and Multiplex Ligation Probe Amplification, respectively.

All results will be shared with patients according to the instructions approved by themselves in the informed consent. A clinical geneticist will discuss results with patients and provide counselling accordingly and will recruit the relatives at risk of inheriting the pathogenic variant with clinical significance. A medical oncologist will explain treatment options if it is appropriate.

Furthermore, genetic counselling will be provided to relatives of patients with germline mutations; we will recommend cancer screening as appropriate.

The study will be conducted at the Instituto Nacional de Ciencias Médicas y Nutrición Salvador Zubirán (INCMNSZ) in Mexico City. Our site is a reference hospital for pancreatic diseases nationwide.

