**Exclusion Criteria:**

- Diagnosed with pancreatic adenocarcinoma more than 6 months before presenting to the clinical site.
- Diagnosed with intraductal papillary mucinous neoplasms, mucinous cystic neoplasms, pancreatic neuroendocrine tumors.

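### Consecutive enrolment at one national pancreatic referral hospital is treated as an unselected Mexican patient population, with no record of why patients were referred

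*Combined protocol and SAP*

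**What the plan says.** The Study design section names a single site and describes it in these words: "Our site is a reference hospital for pancreatic diseases nationwide". Recruitment is consecutive: "Prevalence will be determined by testing all consecutive patients with histologic diagnosis of pancreatic adenocarcinoma (PAC) regardless of family history, clinical stage and treatment". The next sentence draws the inference at issue: "In other words, the prevalence will be determined in an unselected patient population".

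The intended target is wider than the site. The official title places the estimate "in an Unselected Cohort of Patients With Pancreatic Adenocarcinoma in a Mexican Population", and the Problem section states that "it is mandatory to determine the prevalence of germline *BRCA* mutations in Mexican patients with pancreatic cancer". The Hypothesis section expects BRCA1/2 prevalence to be similar to that in other unselected populations, and there describes the sample as unselected with respect to family history.

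The only selection effect the plan names is survival: "To decrease potential survivorship bias, we will include only patients with PAC within 6 months of diagnosis". The exclusion criteria cover late presentation ("Diagnosed with pancreatic adenocarcinoma more than 6 months before presenting to the clinical site") and other histologies. Neither the inclusion nor the exclusion criteria mention a known germline variant, an earlier germline test or the reason for referral. Under Statistical methods, prevalence is a crude proportion of all patients. Family history is described by BRCA status, but prevalence is not estimated by referral route or by what was known before enrolment.

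**The concern.** Two stages decide who enters the sample: who reaches the hospital, and who is enrolled once there. The plan controls the second stage and takes the result as settling both. A nationwide referral centre need not see a representative stream of patients. Family history, a known family variant, age, resectability or fitness to travel could each affect who is sent. Not using family history as an entry criterion does not undo a referral that was made because of it.

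Prevalence is the only primary result, and the hypothesis rests on comparing it with other unselected populations. If referral enriched the sample for carriers, the study could show similarity, or an excess, that does not hold among patients in general. A larger sample from the same site would not reduce this bias, and a confidence interval would not reveal it.

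**Working it through.** **Inputs from the documents.** Statistical methods gives n = 107, assumed prevalence p = 7.5%, precision d = 5 points and 95% confidence. The only carrier rate for familial cases is 17%, for BRCA2 alone, in the title of a cited familial pancreatic cancer series (References). The documents give no share of patients referred for hereditary reasons, so every such share below is an assumption.

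**1. The plan's own figure.** n = z²·p(1−p)/d² = 1.96² × 0.075 × 0.925 / 0.05² = 106.6, which rounds up to 107. The stated size reproduces without the finite population correction that the plan mentions; that is a separate matter. The half-width at n = 107 is 4.99 points.

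**2. Expected carriers.** 107 × 0.075 = 8.0. The estimate from 8/107 is 7.5%, with exact 95% interval 3.3% to 14.2%.

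**3. Prevalence without hereditary referrals.** Suppose 2 or 3 of the 8 carriers were referred for a known variant or suspected hereditary cancer. The answer depends on how many non-carriers were referred for the same reason and leave with them.

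| Carriers removed | Only carriers removed | Removed group has a 17% carrier rate |
|---|---|---|
| 2 | 6/105 = 5.7% | 2/0.17 ≈ 12 removed; 6/95 = 6.3% |
| 3 | 5/104 = 4.8% | 3/0.17 ≈ 18 removed; 5/89 = 5.6% |

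The estimate falls by between 1.2 points (7.5 − 6.3) and 2.7 points (7.5 − 4.8).

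**4. Bias from over-representation.** Let f be the share of the sample that is there only because of such referral, beyond what an unselected cohort would contain, and q the carrier rate in that share. Take 7.5% as the true prevalence. Then observed prevalence = (1 − f) × 7.5% + f × q, and bias = f × (q − 7.5%).

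| q | f = 5% | f = 10% | f = 20% | f at which bias = 5 points |
|---|---|---|---|---|
| 17% | 8.0% | 8.5% | 9.4% | 52.6% |
| 50% | 9.6% | 11.8% | 16.0% | 11.8% |
| 100% (known carriers) | 12.1% | 16.8% | 26.0% | 5.4% |

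At q = 17% the bias is 0.5 to 1.9 points, well inside the planned precision. If the surplus consists of known carriers, 5.4% of 107, or about 6 patients, is enough to match the whole 5 points. The 50% and 100% rows are illustrations; the documents support neither rate.

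**The case against.** The strongest reply is that the plan's use of the word is narrower than it looks. The Hypothesis section ties it to family history, and the Study design section explains it as enrolment without regard to family history, stage or treatment. The primary objective speaks only of a cohort of patients and does not mention Mexico. A reader might infer that the study's formal objective is a national estimate. The documents do not support that: the broad claim is in the title and the Problem section. It is still the claim those sections invite, and the family-history qualifier does not close the gap, because referral can itself depend on family history.

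A reader might also infer that hereditary referrals do occur here and inflate the result. Nothing in the documents shows this. The hospital is described as a centre for pancreatic disease, not for genetics, and selection by fitness or resectability has no stated direction. This part of the objection stands, so the point is one of unmeasured risk.

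Thirdly, a geneticist takes a family history from every patient, so an unusual family-history load could be noticed. That is true, but family history does not say why the patient was sent or whether a variant was already known.

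Finally, patients with known variants or strong family histories belong in any unselected cohort. Only their over-representation is a problem. This also stands, and it rules out replacing the main estimate with one that leaves them out.

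**Conclusion.** The concern holds as a limit on what the estimate represents and as a gap in the data needed to check it. Consecutive enrolment at this site supports a statement about patients seen at this site. It does not by itself support one about Mexican patients with pancreatic cancer.

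The size is unknown. With about 8 expected carriers, 2 or 3 who came through hereditary referral would mean a prevalence 1.2 to 2.7 points lower once that group is left out. Over-representation of 5% to 20% adds 0.5 to 1.9 points at the one familial rate in the documents, and reaches the planned 5 points only with much higher assumed carrier rates or shares. All of this assumes a true prevalence of 7.5% and referral shares that the documents do not give.

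It would go too far to conclude that the planned prevalence is inflated, or that the hypothesis should be judged on a figure without known carriers. Such a figure could be too low, and nothing shows that the comparison populations were restricted in the same way.

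**What to change.** 1. Word the primary conclusion as prevalence among consecutive patients with pancreatic adenocarcinoma at this national referral centre, and qualify the references to a Mexican population accordingly.
2. At the geneticist's existing visit, record the reason for referral and whether a germline variant was already known in the patient or family. Keep these as separate fields: a known variant is not the same as being sent because of it.
3. Keep the all-patient prevalence as the primary figure and as the figure for the comparison in the Hypothesis section. Beside it, prespecify a sensitivity estimate without patients referred because of a known variant or suspected hereditary cancer. Remove carriers and non-carriers alike, and state that the result may under-estimate prevalence.

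The cost is a narrower claim, two extra fields at a visit already planned, and one extra line of analysis on a somewhat smaller denominator. The fields are easier to collect at enrolment than to reconstruct later.
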